
Criteria for enrolment

Definitions

For this study, the following definitions are used:

Enter The act of assessing eligibility of a patient for the study. All patients that are planned for APE or EAPE should be entered (registration). The registration process can be performed before enrolment/randomization (recommended) or at the same time automatically when doing enrolment/randomization (or postoperatively for those not randomised/enrolled).

Enrol The act of assigning a patient to a treatment alternative by randomization in the study. When the randomization is done on the web application the patient is registered with status entered and enrolled. The informed consent document must be signed by the patient before enrolment.

Register entry without randomization

If the patient cannot be enrolled (randomised) because of intraoperative or preoperative circumstances the entry must be registered via the web application without randomization. Choose “registration of entry with no randomization”. All patients that undergo APE or EAPE in participating

centres during the inclusion phase of the study must be registered via the web application where information of eligibility is registered.

Registered patients

All patients registered (entered and enrolled or only entered) are those who are assessed for eligibility when they are planned for APE or EAPE during the inclusion phase of the study.

Recommended procedure

We recommend that a study nurse enter/register a patient immediately after a MDT conference where a decision of either APE or EAPE is made. We also recommend that the patient should be informed early, in conjunction with the invitation to a preoperative visit, about being included in the study register and national colorectal cancer register during the process.

Later when the surgeon examines the patient preoperatively, the patient can be informed about the study, asked about participation, informed consent can be obtained, and the patient can be enrolled/randomised if an EAPE operation is decided and criteria fits. The randomization can be postponed to the operating room (intra-operative randomization) if there is uncertainty of fulfilment of inclusion criteria up till this point.

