If the patient refuses participation and do not want registration or enrolment and the registration was already done by the nurse, a request of erasing the registration should be communicated with the study administration. This applies only for patients that do not want to be registered. Note that patients can refuse enrolment in the study but still accept registration that simply means that the study administration knows about that an APE or EAPE operation is planned or executed. In these cases the registration stays but the patient is not randomised/enrolled.

We recommend that during the inclusion phase of the study, the study nurse do a weekly check-up for patients operated during the past week with APE or EAPE. The nurse should secure that all these patients are either randomised or registered with limited but correct data on the study homepage at www.norrlandskirurgi.se. The data for nonrandomised patients will be final at this stage and the data is later necessary for the CONSORT diagram of final reports.

[figure not shown]

Figure 1. Illustration of study design and patient flow to operation.

Eligibility for enrolment

Inclusion criteria

Adult (18 years or older) rectal cancer patients where **wide resection** of pelvic floor muscles together with rectum and anal canal **have made reconstruction of pelvic floor necessary** i.e. primary suture of pelvic floor in the midline is not possible. Resection of coccyx is optional.

Exclusion criteria

1. Age less than 18 years
2. Very large resections including partial resection of sacrum and patients considered for bilateral flap reconstruction
3. Large concomitant resection of vaginal wall where total (vaginal) wound closure is not an option
4. Expected survival less than one year at operation
5. Patient do not sign informed consent document, this group includes:
 - a. Patients that do not want to participate and undergo allocation to treatment by randomization
 - b. Patients or their legal representatives do not fully understand the role of participation

Violation of criteria for enrolment

The criteria for enrolment must be followed explicitly. If a patient who does not meet eligibility criteria is inadvertently enrolled, that patient should be discontinued from the study and the PI of the central study administration must be informed. See about discontinuations below.

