The study aims to enrol a high proportion (>60 %) of eligible patients. Centres that fail to register patients operated on with either APE or EAPE and fail to enrol eligible patients will be discontinued from the study. The study administration claims the right to take part of data from participating centres revealing numbers of performed APE and EAPE operations during the inclusion phase.

Disease diagnostic criteria

The diagnosis of rectal malignancy should be determined by histology before enrolment but absence of definitive histology is not an exclusion criterion if the decision of operation leans on sound clinical judgement. Primary cancer of rectum is defined as a malignancy that is not treated with curative intention before the operation. The definition allows preoperative oncologic treatments if the plan is to cure the patient with surgery. Recurrent cancer is defined as a cancer that develops after a previous treatment with curative intention. The previous treatment does not have to be surgical.

Patient assignment

After patients give written informed consent and meet criteria for enrolment they may be randomised to one of the study arms before the operation if the extended APE procedure is decided and will be executed. If there is any doubt of the suitability of the procedure and the definitive decision of extended APE is done in the operating room, the randomization can be done intra-operatively. In these cases written informed consent must be given before the operation and the patient is informed that the assignment is decided later during the operation.

The randomization will be done on-line via the study homepage web application at www.norrlandskirurgi.se

Discontinuations

1. If a patient who does not meet eligibility criteria is inadvertently enrolled, that patient should be discontinued from the study.
2. If a centre has an unacceptably low proportion of registrations (entry) and/or enrolments there is a substantial risk for selection bias of study patients and the centre with its patients will be discontinued from the study.
3. Inevitable discontinuations, as if patients decease or are lost to follow up are registered by site investigator via the web application.
4. The patients are allowed to discontinue from the study without any reason if they wish according to ethical standards. If a patient chooses to discontinue from the study he/she should be asked if the study data collected until this point can be used or should it be erased.

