
All discontinuations should be registered via the study homepage web application at www.norrlandskirurgi.se Result data from patients discontinued for reason 1-2 (above) will be erased and is not included in final analysis. Result data from patients discontinued for reason 3 (above) can be used until the date of discontinuation. Result data from patients discontinued for reason 4 (above) can be used until the date of discontinuation or all data will be erased depending on the patient's decision.

Surgical methods

Preoperative measures

All patients should receive prophylactic antibiotic before the operation. One dose preoperatively is our recommendation but if the operation takes more than 4 hours to complete a second dose should be given within 24 hours from the first dose[13, 14]. If a 2nd generation cephalosporine is used alone, 2 additional doses every 8 hours after the first dose should be used [15]. Antithrombotic prophylaxis should be given with low molecular weight heparin and it should be continued 28 days[16-20]. Enhanced recovery programs may be used in whole or partially but the program or routines chosen by a clinic should not change during the study period. The patient should be informed about the postoperative rehabilitation programme by the physiotherapist. One of two available rehabilitation programmes should be chosen and used for all patients during the whole study period. See postoperative rehabilitation programmes below.

First part of the operation

The following technique description is cited directly from the publication of Holm et al.[7] The abdominal part of the operation is performed as in conventional APR, with one important modification: the mesorectum is not dissected off the levator muscle. Thus the mobilization is stopped at the upper border of the coccyx posteriorly, just below the autonomic nerves laterally and anteriorly just below the vesicles in men or just below the cervix uteri in women. The divided left colon is brought out to form a colostomy and the abdomen is closed.

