We consider that a minimally important clinical effect applies for this study if results differ less than 10%. The noninferiority margin is thus set to 10%. This means that the results from study arms are considered clinically having no important differences if the results from test operation (APCI) differ less than 10% in the main outcome. We claim noninferiority for test operation if the result will be in the range less than 10% inferior result up to a trend for superior result but not statistically significant for the main outcome. If the result shows a statistically significant difference we claim superiority (or inferiority) of the test operation. If we find noninferiority based on the main outcome we may still draw conclusions about which operation should be preferred, based on results from secondary outcomes.

Data to be analyzed

All primary analyses in this study will be performed according to the intent-to-treat (ITT) principle, that is, patients will be allocated to treatment groups corresponding to their assigned treatment, even if the patient does not receive the correct treatment.

The intention-to-treat population will consist of all randomised patients who are operated with EAPE.

Per-protocol analyses are secondary and may be used if special circumstances motivate to use such. If noninferiority is to be stated we will do a per-protocol analysis in addition to the ITT analysis and if both analyses are non significant it will give more evidence of noninferiority. The per-protocol population will consist of all patients in the intent-to-treat population who have met all protocol requirements and who have successfully completed the trial up till one year.

Patient disposition

Reasons for discontinuations in the study will be compared between the 2 treatment groups. Result tables or the Consort[24] diagram will reveal the number and proportion of patients who have completed the study as well as patients that have discontinued, grouped by reason for discontinuation.

Patient characteristics

Age, gender, primary or recurrent rectal cancer will be registered when the patient is randomised via the web application and will be included in the summary reports.

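### The set called intention-to-treat omits randomised patients not operated with EAPE, and data of those later found ineligible are erased, so exclusions after open allocation can depend on the arm

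*Protocol*

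**What the plan says.** Protocol, Data to be analyzed, first states the principle: "patients will be allocated to treatment groups corresponding to their assigned treatment, even if the patient does not receive the correct treatment". The next paragraph defines the population: "The intention-to-treat population will consist of all randomised patients who are operated with EAPE".

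Protocol, Violation of criteria for enrolment and Discontinuations (reason 1): "If a patient who does not meet eligibility criteria is inadvertently enrolled, that patient should be discontinued from the study". Enrolment here means randomisation; the Definitions describe it as "The act of assigning a patient to a treatment alternative by randomization in the study".

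Protocol, Discontinuations (reason 2): where a centre's proportion of registrations or enrolments is judged too low, "the centre with its patients will be discontinued from the study". No cut-off is attached. The nearest figure is an aim under Violation of criteria for enrolment: "The study aims to enrol a high proportion (>60 %) of eligible patients".

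For both reasons the end of Discontinuations adds: "Result data from patients discontinued for reason 1-2 (above) will be erased and is not included in final analysis".

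On timing, Patient assignment says of consented patients that "they may be randomised to one of the study arms before the operation if the extended APE procedure is decided and will be executed"; randomisation in the operating room is the option when there is doubt. Blinding states that surgeon, examiner and patient need not be blinded. Safety analyses bases the between-arm safety comparisons on the same ITT population.

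**The concern.** An intention-to-treat set protects the randomised comparison because membership is fixed at randomisation. Here membership also depends on two later events: whether EAPE was carried out, and whether someone later judged the patient ineligible. Both can be decided by people who know the allocation. If those decisions differ between arms, the groups analysed are no longer the groups randomised, and the result can move in either direction.

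Erasure makes this irreversible. If the data were merely left out of the primary analysis, the effect of the exclusions could be checked by adding them back. Once erased, they cannot be recovered by any statistical analysis plan, so this cannot be left to a later document.

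**Working it through.** **1. The rules side by side.** The declared principle keeps patients who did not receive the correct treatment. The population definition keeps only those operated with EAPE, which is known only after randomisation. Reasons 1 and 2 remove further randomised patients. The definition and the erasure rule both contradict the principle.

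**2. Can exclusion depend on the arm?**
- The Flowchart permits randomisation at the preoperative visit and lists an eligibility check again at the operation, by the surgeon who must follow the allocation.
- The inclusion criterion turns on whether the pelvic floor can be closed in the midline after the resection, which is settled during surgery. An exclusion criterion covers patients considered for a bilateral flap; it is plausible, though not documented, that this question arises more readily in the flap arm.
- No assessor blind to allocation is named, and no time limit is set for declaring a patient ineligible.

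So the text allows arm-dependent exclusion. It does not show that this would happen.

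**3. The planned sample size, as a base.** Inputs from Sample size: 63% and 30% low performance, 90% power, alpha 0.05 (taken as two-sided), 20% loss. With unpooled variance,

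n = (1.960 + 1.282)² × (0.63×0.37 + 0.30×0.70) / 0.33² = 42.8, so 43 per arm; 43/0.8 = 53.75, so 54 per arm and 108 in total.

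The same formula at 80% power gives 32 per arm, 40 after loss, and 80 in total. Both planned figures are reproduced.

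**4. What selective exclusion could do (illustration only).** Assume 43 evaluable patients per arm, no true difference, and k low performers removed from the APCI arm alone. The shift in that arm's rate is p − (43p − k)/(43 − k). The type I error is that of a two-sided pooled z-test, computed over the binomial distributions.

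| k | shift, p = 46.5% | type I error, p = 46.5% | shift, p = 63% | type I error, p = 63% |
|---|---|---|---|---|
| 0 | 0 | 4.9% | 0 | 5.5% |
| 2 | 2.6 points | 6.4% | 1.8 points | 5.7% |
| 4 | 5.5 points | 8.9% | 3.8 points | 6.2% |
| 6 | 8.7 points | 13.9% | 6.0 points | 8.9% |

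This scenario is deliberately one-sided. The documents give no k.

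**5. Centre erasure.** Under Summary of study design, randomisation is in blocks and stratified by centre, so removing a centre takes out both arms about equally. The loss is in power. If m patients are erased on top of the 20% loss, the evaluable number per arm is 0.8 × (108 − m)/2:
- m = 6: 40.8 per arm, power 88.6%
- m = 12: 38.4 per arm, power 86.7%
- m = 18: 36.0 per arm, power 84.5%

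With no centre erased there are 43.2 per arm and power is 90.3%. Six is the capacity that the protocol asks of a centre over three years; a centre removed for low enrolment may have fewer. The trigger is also worded inconsistently: Violation of criteria for enrolment requires failure to register and failure to enrol, whereas Discontinuations accepts either.

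**6. What keeping everyone costs.** Assume a share f of each arm has no EAPE and the same low-performance risk in both arms (30% to 63% tried). The difference becomes 0.33 × (1 − f). With 43.2 evaluable per arm:

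| f | difference | power | total N for 90% power |
|---|---|---|---|
| 5% | 31.4 points | about 87% | 120–124 |
| 10% | 29.7 points | about 83% | 136–138 |
| 15% | 28.1 points | about 78% | 154–156 |

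**The case against.** The strongest reply is that the protocol contains safeguards and the numbers may be small. Preoperative randomisation is meant only for patients in whom EAPE is decided; doubtful cases can be randomised during surgery. Reasons for discontinuation are to be compared between arms. The EAPE condition concerns the resection, so a patient given the other reconstruction stays in the assigned arm. On this view the set is a mislabelled modified ITT, not an abandonment of the principle.

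Much of this stands: the EAPE restriction probably affects few patients. It does not answer the erasure of patients found ineligible. Intra-operative randomisation is optional and helps only where doubt was recognised beforehand, and tabulating reasons can reveal an imbalance but cannot correct it once the data are gone.

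A reader might infer three stronger things that the documents do not support:
- That erasing a centre destroys the comparability of the arms. Stratification by centre largely prevents this. Nor does any section say that results are reviewed when a centre is removed, and efficacy interim analyses are foreseen only if inclusion exceeds five years. What remains is a discretionary rule with no cut-off.
- That the safety data are lost altogether. Swedish units record complications and adverse events in the national registry, reports are evaluated continuously, and an independent review takes place yearly. The narrower point holds: erased patients leave the between-arm ITT safety comparison.
- That the bias would use up a given part of the noninferiority margin. This needs assumed removal rates, removal from one arm only, and a reading of 10% as percentage points, which the protocol does not state; its primary outcome is in seconds.

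**Conclusion.** The point holds for the two patient-level rules. As written, the ITT definition contradicts the declared principle, and the erasure of randomised patients found ineligible allows arm-dependent exclusion that no later analysis could undo. This should be corrected, and the wording change is cheap. Centre erasure is a lesser fault: it costs power, data and transparency more than comparability.

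The size of any bias cannot be known from the document. The illustration shows only that a handful of selective removals from about 43 patients would matter: four would take the type I error from 4.9% to 8.9% at a 46.5% rate, but only from 5.5% to 6.2% at a 63% rate. The planned sample size is not in dispute.

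**What to change.** 1. Data to be analyzed: define ITT as all validly consented randomised patients, analysed in the assigned arm whatever operation was done and whatever a later eligibility review finds.
2. Discontinuations: remove erasure for reasons 1 and 2. Erase only at the patient's own request or where valid consent was never given; the second exception is needed because missing consent is itself an exclusion criterion and so falls under reason 1.
3. Violation of criteria for enrolment, and reason 1: an ineligible patient is reported to the central study administration and stays in follow-up and analysis.
4. Reason 2: a failing centre stops recruiting; its randomised patients stay in follow-up and in all efficacy and safety analyses.
5. Report eligible patients operated with EAPE as a named modified-ITT sensitivity set, and require it to agree with ITT before noninferiority is claimed. Patients given neither reconstruction pull the arms together, which favours that claim. The per-protocol analysis already planned for noninferiority helps, but it also demands completion to one year and so does not replace this set.

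The cost is an amendment of wording, continued follow-up of the patients concerned, and some dilution. On the assumptions above, power is about 87% if 5% have no EAPE and 83% if 10% do, so the sponsor should state the share it expects and consider whether 108 is still enough.
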